8.3 Analysis of other efficacy variables

- Absolute and percentage change from Baseline in PASI with time (Week 2 to Week 36)
- PASI75, PASI90 and PASI100 response at Weeks 2, 4, 8, 12, 20, 24, 28 and 36
- PASI25 and PASI50 response (Week 2 to Week 36)
- IGA response (Clear or Almost Clear with at least 2-category improvement from Baseline) at Weeks 2, 4, 8, 12, 20, 24, 28 and 36
- Change from Baseline in IGA score with time (Week 2 to Week 36)
- Change from Baseline in the BSA affected by psoriasis with time (Week 2 to Week 36)
- Change from Baseline in HADS-A and HADS-D scores with time (Week 4 to Week 36)
- Percentage of subjects with scores below 8 in HADS-A and HADS-D (subjects with normal scores) at each post-Baseline visit (Week 4 to Week 36)

Tabulations and figures will be based on the FAS and listings will be based on the SS.

8.3.1 Psoriasis Area and Severity Index

The absolute values and percentage change (improvement) from Baseline in the PASI score will be summarized as described in [Section 8.1.2](#).

The PASI25 and PASI50 responses are based on at least 25% and 50% improvement from Baseline in the PASI score. Thus, the following will apply:

- If the percentage improvement is $\geq 25\%$ then the subject is a PASI25 responder
- If the percentage improvement is $\geq 50\%$ then the subject is a PASI50 responder (and is a PASI25 responder also)

The definitions of PASI75, PASI90 and PASI100 response are provided in [Section 8.2.1](#). Subjects meeting the definition for PASI75, PASI90 and PASI100 response are also considered as PASI25 and PASI50 responders at the respective visit.

The number and percentage of subjects achieving a PASI25, PASI50, PASI75, PASI90 and PASI100 response will be tabulated by treatment group and visit. The 95% CI for the percentage of responders will be calculated using a Wilson approximation and included in the tabulation. In addition, the percentage of responders (including 95% CI) will be plotted at each post-Baseline visit for each response variable. Separate plots will be presented for each of PASI25, PASI50, PASI75, PASI90 and PASI100 with both treatment groups overlaid on the same plot

Missing data will be imputed using NRI as described in [Section 4.2.1.1](#). Subjects with missing data will be regarded as nonresponders for each of the response variables. Missing data will not be imputed for the listing.

The tables and figures for PASI response variables will also be repeated using observed cases and will include a category for missing data; subjects who enroll in the extension study or those who discontinue will be counted in the missing category for this tabulation where applicable. For this tabulation based on observed cases the denominator for the percentage of responders and nonresponders will be the number of subjects with nonmissing data at the visit.

The individual PASI scores will be listed as described in [Section 8.1.2](#). Subjects achieving a PASI25 and PASI50 response at each visit will be flagged in the listing.

8.3.2 Investigator's Global Assessment

The IGA results will be listed by subject and visit as described in [Section 8.2.2](#). Subjects achieving a clinical response (clear [0] or almost clear [1] with at least a 2-category improvement from Baseline) at each visit (Weeks 2, 4, 8, 12, 20, 24, 28 and 36) will be flagged in the listing as responders.

The number and percentage of responders at each post-Baseline visit (Weeks 2, 4, 8, 12, 20, 24, 28 and 36) will be summarized by treatment group as described in [Section 8.2.2](#). The 95% CI for the percentage of responders will be included, calculated using a Wilson approximation. The percentage of responders (with 95% CI) will also be plotted over time.

Missing data for the IGA response at a specific visit will be imputed using NRI as described in [Section 4.2.1.3](#). Subjects with missing data will be regarded as nonresponders for the analysis. Missing data will not be imputed for the listing. The table and figure will also be repeated using observed cases and will include a category for missing data; subjects who enroll in the extension

study or those who discontinue will be counted in the missing category for this tabulation where applicable. For this tabulation based on observed cases the denominator for the percentage of responders and nonresponders will be the number of subjects with nonmissing data at the visit.

In addition to the IGA responder tabulations, shift tables will be presented including the change in IGA individual scores at Week 8, Week 16 and Week 24, compared to the Baseline score. In addition, a frequency table will be presented showing the number and percentage of subjects with each specific IGA score at each visit. Both tabulations will include a category for missing data. The denominator for the percentages will be the number of subjects in the FAS, for each treatment group.

8.3.3 Body surface area

The percentage BSA (0 to 100%) affected by psoriasis will be listed by subject and visit including the percentage change from Baseline. Descriptive statistics will be presented by treatment group and visit for both absolute values and percentage changes from Baseline.

For subjects that discontinue the study or those that enter the extension study, missing data will be imputed using LOCF for the tabulations as described in [Section 4.2.1.2](#). Missing data will not be imputed for the listing.

Tabulations (absolute values and percentage change from Baseline) will also be repeated using observed cases.

8.3.4 Hospital Anxiety and Depression Scale

The HADS scores for anxiety (HADS-A) and depression (HADS-D) each range from 0 to 21 with higher scores indicating worse state. A score below 8 is considered to be normal whereas a score of 15 and above is considered severe (Snaith and Zigmond, 1994). The individual items, associated item scores and calculation rules for the anxiety and depression domains are provided in [Section 14.2](#).

The results of the HADS will be listed by subject and visit including the individual item responses and the derived domain scores for anxiety (HADS-A) and depression (HADS-D). Changes from Baseline will be calculated based on the domain scores only, and will be included in the listing.

Descriptive statistics will be presented by treatment group and visit for both absolute values and changes from Baseline, separately for each domain (HADS-A and HADS-D). The number and percentage of subjects with scores <8 for the HADS-A and HADS-D will be summarized by treatment group at each visit. The percentages will be based on the number of available observations at each visit; the number of subjects with missing data (including subjects who enroll in the extension study) will be included in the tabulation.

There will be no imputation of missing data for the HADS scores, either for the descriptive statistics or frequency tables.

9 PHARMACOKINETICS AND PHARMACODYNAMICS

9.1 Pharmacokinetics

There will be no calculation of PK parameters for this study. The analysis of PK data for this study will focus on the concentrations of bimekizumab only.

The actual blood sampling times for bimekizumab concentrations will be obtained relative to the start time of the first injection and will be reported in weeks to 1 decimal place. Individual blood sampling times and concentrations of bimekizumab will be listed by treatment group for the SS and will include the actual sampling time in weeks relative to the first dose.

Individual concentrations will be summarized by treatment group at each scheduled visit based on the PK-PPS, using n, mean, median, SD, minimum, maximum, geometric mean, 95% CI for the geometric mean and geoCV (assuming log-normally distributed data).

Individual concentration versus time (week) profiles will be presented graphically in linear and semi-logarithmic scale with all subjects overlaid on the same plot (spaghetti plots) and separate plots for each treatment group. Geometric mean profiles of bimekizumab will also be presented on both linear and semi-logarithmic scale respectively with and without the corresponding lower and upper limit of the 95% CI for linear and semi-logarithmic plots respectively. Both treatment groups will be overlaid on the same plot. All figures will include the LLOQ on the semi-logarithmic plots.

The following rules will apply for PK data listings and summaries:

- Values below the LLOQ will be reported as BLQ
- Descriptive statistics of concentrations will be calculated if at most 1/3 of the individual data points are missing or are not quantifiable (<LLOQ). Values that are BLQ will be replaced by the numerical values of the LLOQ/2 in this instance. However, if $n \leq 3$ or more than 1/3 of the individual data points are missing or are not quantifiable, then only n, minimum and maximum will be presented. The other descriptive statistics will be left blank.
- The 95% CI for the geometric mean should be left blank if the SD (or equivalently, the geoCV) is 0
- The geoCV will be calculated using the following formula where SD is the standard deviation from the log-transformed data

$$geoCV = [100x\sqrt{(e^{SD^2} - 1)}] \quad [10]$$

Additional rules for handling values that are BLQ are described in [Section 4.2.3](#).

9.2 Pharmacodynamics

The results of the PD assessments (flow cytometry variables) will be listed by treatment group and subject (based on the SS) including changes from Baseline.

Absolute values and changes from Baseline will be summarized (including 95% CI) by treatment group based on the PD-PPS.

Figures of mean and mean changes from Baseline (including 95% CI) will be presented with separate plots for each variable and both treatment groups overlaid on the same plot.

The list of flow cytometry variables to be measured is provided in [Section 14.3](#).

9.3 Pharmacokinetic/pharmacodynamic analyses

A pooled PKPD analysis will be performed by combining the data from this study (PS0016) with the data from PS0010. The methodology for the PK/PD analysis will be described in a separate

data analysis plan (DAP). The results of the analysis will be reported in a separate PK/PD report and added as an appendix to the CSR.

10 IMMUNOLOGICAL ANALYSES

The results for the ADA measurements will be listed by treatment group and timepoint based on the SS, including the Screening assay, confirmatory assay and titre (if applicable).

A cut point will be determined by the bioanalytical laboratory that will be used to determine the status of ADA as above the cut point (ACP) or below the cut point (BCP). For any ADA levels that are ACP, a further confirmatory assay will be performed, the results of which will be determined as either 'confirmed positive' (CP) or 'not confirmed positive' (NCP). For samples that are CP, a further titre assay will be performed and the ADA titre will be reported.

The following definitions will be applied:

- An ADA status of positive will be concluded for any subject with an ADA level that is ACP and CP at any timepoint
- An ADA status of negative will be concluded for any subject with an ADA level that is either BCP or ACP and NCP at any timepoint
- A subject will be classified as having ADA positivity at Baseline if the Day 1, predose result is ACP and CP
- A subject will be classified as having treatment-induced ADA positivity when meeting one of the following criteria:
 - The Baseline result is either BCP or ACP and NCP, and at least one post-Baseline timepoint is ACP and CP
 - The Baseline result is positive (ACP and CP) and at least one post-Baseline measurement shows a pre-defined fold increase in titre from the Baseline value (the fold increase from Baseline required to meet this criteria will be defined with the development of the assay and will be included in the TFLs)
- A subject will be classified as overall positive if at least one post-Baseline measurement is ACP and CP (this includes subject who have negative results at Baseline)
- A subject will be classified as overall negative if at all post-Baseline visits the ADA status is negative (this includes subjects who have positive [ACP and CP] results at Baseline)

The ADA status (positive/negative) will be summarized as a categorical endpoint (number and percentage of subjects) by treatment group for all timepoints and overall, based on the SS.

In addition, the first occurrence of treatment-induced ADA positivity (based on the definitions above) will be summarized (number and percentage of subjects) by treatment group at each post-Baseline visit, based on the SS. This tabulation will count the number of subjects at each post-Baseline visit who fulfill at least one of the above defined criteria for treatment-induced positivity; subjects will be counted in the numerator based on the earliest visit at which one of these criteria is fulfilled. At other visits, subjects will be counted in the denominator (assuming a measurement is available). For all tabulations, percentages will be based on the number of observations at each visit.

A separate listing will be presented (based on the SS) showing the bimekizumab concentrations and ADA measurements in the same output in adjacent columns. The listing will include the bimekizumab concentration, ADA status (ACP or BCP) and confirmatory assay results if applicable (NCP or CP), together with the titre for results that are CP. In addition, the time since the previous administration of IMP will be reported (in days).

Finally, individual subject plots will be presented displaying the PASI total score, ADA titre and bimekizumab concentrations overlaid on the same figure. The figure will also show the timing and dose of each administration of bimekizumab (or placebo) received during the study. The ADA data will be plotted using a semi-logarithmic scale.

The rules for handling values that are BLQ in the bimekizumab concentration data are described in [Section 4.2.3](#). For the ADA data, any negative results for which there are no titres available at a specific visit will be substituted with 0.001 for the purpose of the figure.

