### 2.2.1 Clinical

Three clinical studies of bimekizumab have been completed: UP0008 in 39 subjects with mild to moderate plaque psoriasis, RA0124 in 30 healthy volunteers, and PA0007 in 53 subjects with psoriatic arthritis. Two studies (RA0123 and UP0031) are ongoing in subjects with moderate to severe rheumatoid arthritis and in healthy subjects, respectively.

UP0008 was a Phase 1, single ascending dose study in adults with mild to moderate psoriasis affecting  $\leq 5\%$  BSA. In this blinded study, single doses of up to 640mg (approximately 8mg/kg in an 80kg adult) were evaluated without any safety concerns. A total of 26 subjects with psoriasis with less than 5% of body surface involvement were treated with a range of single iv doses from 8 to 640mg. There were no clinically relevant safety findings identified at any dose and all doses were well tolerated. The pre-specified exploratory assessment of disease activity showed clinically relevant and statistically significant improvements at the higher doses studied.

RA0124 was a Phase 1, open-label, parallel-group, single-dose study in healthy subjects. The primary objective of this study was to determine the absolute bioavailability of single sc doses of bimekizumab (80mg and 160mg). The secondary objectives were to evaluate the dose proportionality of bimekizumab 80mg and 160mg sc, and to evaluate the safety and tolerability of these sc doses and 160mg given by iv infusion. In RA0124, the absolute bioavailability was

similar for the 2 doses tested (0.656 and 0.631 for the bimekizumab 80mg and 160mg sc doses, respectively). The PK of bimekizumab was linear in the tested dose range and the median  $t_{1/2}$  following sc administration was similar to that following iv administration (27.81 days and 28.25 days for bimekizumab 160mg sc and 160mg iv, respectively).

Bimekizumab has also been investigated in a Phase 1b, proof of concept, randomized, placebo-controlled, multiple dose study (PA0007). The primary objective of PA0007 was to assess the safety and PK of multiple dose administration of iv bimekizumab in subjects with psoriatic arthritis. Four active doses and a placebo were tested. Drug was administered as a loading dose at Week 0, and 2 additional doses were administered at Week 3 and Week 6. In each treatment group, subjects received a total of 3 doses of bimekizumab, administered every 3 weeks as shown below:

- 80mg loading dose followed by 40mg at Weeks 3 and 6

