##### Treatment Period

During the Treatment Period, subjects will be randomized 2:1 to receive the following blinded study treatment regimens:

- Treatment arm A: Bimekizumab 320mg administered sc at Baseline and Week 4, and placebo administered at Week 16
- Treatment arm B: Bimekizumab 320mg administered sc at Baseline and Weeks 4 and 16

There will be approximately 30 subjects in treatment arm A and 15 subjects in treatment arm B. Bimekizumab will be administered in the clinic at Baseline and Week 4, and at Baseline, Week 4, and Week 16 for those in treatment arm A and treatment arm B, respectively. Additional

nondosing study visits will occur at Week 2, Week 8, Week 12, Week 20, Week 24, and Week 28.

From Week 20 through Week 28, subjects who were previously PASI25 responders but subsequently relapse (defined as returning to a less than PASI25 response) will undergo the study assessments for that visit (ie, Week 20, Week 24, or Week 28) before receiving their first dose of study treatment in the extension study at Week 20, Week 24, or Week 28. Subjects eligible for the extension study must have the assessments for SFU conducted prior to entering the extension study. Subjects who have not achieved a PASI25 response at any visit prior to Week 20 will not be eligible to enter the extension study. All subjects not enrolling in the extension study will continue in PS0016 until the SFU Visit at Week 36.

Subjects withdrawing early from the study will undergo the Early Withdrawal Visit assessments (ie, Week 36) and will enter the SFU Period.

The assessments at each Treatment Period Visit are presented in [Table 5-1](#).

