## **11 ASSESSMENT OF IMMUNOLOGICAL VARIABLES**

### **11.1 Assessment of immunogenicity**

Blood samples for measurement of antibodies to bimekizumab will be collected at the visits specified in Table 5-1. The threshold for antibody positivity will be defined prior to analysis.

At dosing visits, blood samples will be drawn prior to dosing, and will be drawn at the same time of the sampling for clinical laboratory tests. The time and date of collection will be recorded in the eCRF.

Instructions pertaining to sample collection, processing, storage, labeling, and shipping are provided in the laboratory manual for this study. The presence of antibodies to bimekizumab will be determined using a validated bioanalytical method. Detailed information on sample analysis will be provided in a bioanalytical report.

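### Anti-bimekizumab antibody (ADA) status is set from assay results without regard to the drug level in the same sample, and expected drug levels are about 6 times higher in Arm B from Week 20

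*SAP*

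**What the plan says.** SAP section 10 sets up a tiered assay. The laboratory fixes a cut point, and samples above it are tested again: "For any ADA levels that are ACP, a further confirmatory assay will be performed". A confirmed sample is positive and gets a titre. For everything else the rule is "An ADA status of negative will be concluded for any subject with an ADA level that is either BCP or ACP and NCP". At subject level, "A subject will be classified as overall negative if at all post-Baseline visits the ADA status is negative". The SAP adds that this includes subjects who were confirmed positive at Baseline.

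The resulting status is tabulated by treatment group at each timepoint and overall. First treatment-induced positivity is tabulated by visit. SAP section 11.2.3 stratifies treatment-emergent adverse event (TEAE) rates by overall ADA status, in two groups.

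Concentration is used only for display. The SAP plans a listing "showing the bimekizumab concentrations and ADA measurements in the same output in adjacent columns", which also gives time since the previous dose, and individual plots of PASI, ADA titre and concentration. Protocol section 11.1 says "The presence of antibodies to bimekizumab will be determined using a validated bioanalytical method" and "Detailed information on sample analysis will be provided in a bioanalytical report". Neither document mentions drug interference, a drug-tolerance limit or an inconclusive result.

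**The concern.** A negative assay result is informative only if the assay could have detected antibody at the drug level present in that sample. If circulating drug binds the antibody and the assay does not tolerate that much drug, a positive subject reads as negative. The SAP files that sample with the true negatives.

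The design makes this more than a uniform loss of sensitivity. Arm A's last active dose is at Week 4 and Arm B's at Week 16, so from Week 20 the two arms are sampled at different drug levels. An ADA percentage that is lower in Arm B after Week 16, or that rises with time in Arm A, could then reflect real immunogenicity, drug interference, or both. The planned tables could not separate them. Immunogenicity is part of a secondary objective and has its own primary variable (Protocol sections 3.2 and 4.1.3). With 15 and 30 planned subjects, one misclassified subject moves Arm B by 1/15 = 6.7 points and Arm A by 1/30 = 3.3 points.

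**Working it through.** **Inputs**
- Half-life (Protocol 2.2.1, single dose, healthy volunteers): "27.81 days and 28.25 days for bimekizumab 160mg sc and 160mg iv, respectively".
- Arm A (Protocol 5.1.1): "Treatment arm A: Bimekizumab 320mg administered sc at Baseline and Week 4, and placebo administered at Week 16". Arm B receives active drug at all three visits. Active doses therefore fall on days 0 and 28 (A) and days 0, 28 and 112 (B).
- ADA samples (Protocol Table 5–1): Baseline and Weeks 4, 8, 12, 16, 20, 24, 28 and 36, which is 8 post-Baseline samples, taken predose at dosing visits. Concentration is sampled at each of these visits.
- Assumed: linear one-compartment decay, with linearity (reported over 80 to 160 mg) extending to 320 mg.

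**The protocol's own figure.** Inclusion criterion 7 equates 20 weeks with about 5 half-lives. 5 × 27.81 / 7 = 19.9 weeks and 5 × 28.25 / 7 = 20.2 weeks, so this is reproduced.

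**Expected level.** As a fraction of one dose's initial level, C(t) = Σ 2^(−(t − t_dose)/h), summed over active doses already given. With h = 28 days:

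| Week | Arm A | Arm B | B/A |
|---|---|---|---|
| 4 (predose) | 0.50 | 0.50 | 1 |
| 8 | 0.75 | 0.75 | 1 |
| 12 | 0.375 | 0.375 | 1 |
| 16 (predose) | 0.188 | 0.188 | 1 |
| 20 | 0.094 | 0.594 | 6.3 |
| 24 | 0.047 | 0.297 | 6.3 |
| 28 | 0.023 | 0.148 | 6.3 |
| 36 | 0.006 | 0.037 | 6.3 |

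At Week 20, for example, A = 2^−5 + 2^−4 = 0.094, and B adds 2^−1 to give 0.594.

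**Ratio from Week 20.** B/A = 1 + 2^(112/h) / (1 + 2^(28/h)), which does not depend on the visit. At h = 28 it is 1 + 16/3 = 6.3. At 27.81 days it is 6.4, and at 28.25 days 6.2. Over an assumed range, 35 days gives 4.4, 30 days 5.6, 24 days 8.8 and 20 days 14.3. Adding first-order absorption with an assumed half-life of up to 5 days changes little: at Week 20, 6.2 instead of 6.4 for h = 27.81, and 6.0 instead of 6.2 for h = 28.25.

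**What an interference threshold would do.** The limit is unknown, so take it as an assumed fraction of one dose's initial level. Of the 8 post-Baseline visits, those at or above it are:

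| Assumed limit | Arm A | Arm B |
|---|---|---|
| 20% | 3 | 5 |
| 10% | 4 | 7 |
| 5% | 5 | 7 |
| 2% | 7 | 8 |

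**Subject level.** A subject followed to Week 36 gives a last sample 32 weeks (8 half-lives) after the last active dose in Arm A, or 20 weeks (5 half-lives) in Arm B. A relapser who enters the extension at Week 20, 24 or 28 has the follow-up assessments then and gives no Week 36 sample. At Week 20 the expected level is 0.594/0.037 = 0.094/0.006 ≈ 16 times the Week 36 level (exactly 2^4). Such a subject can still be classed as overall negative.

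A false-negative rate cannot be calculated, because the documents give neither a tolerance limit nor an expected ADA rate.

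**The case against.** The strongest reply is that harm is not shown. The method is to be validated, with assay detail left to a bioanalytical report. If tolerance exceeds study concentrations, this cause produces no false negatives. The listing and individual plots let a reader find negatives at high drug levels by hand among about 45 subjects. Exposure is the same in both arms for four of the eight post-Baseline visits. A false overall negative requires every post-Baseline sample to be negative, including Week 36 for those who reach it. No test is planned on ADA.

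All of that stands and limits the point. It does not remove it: inspection of a listing corrects neither the by-arm counts nor the TEAE strata. An unknown tolerance limit is a reason for a conditional rule, since that rule does nothing if the limit is never exceeded.

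Three stronger readings are tempting, and the documents do not support them:
- A reader might infer that negativity rests on the cut point alone. It does not, because samples above the cut point go to a confirmatory assay. That tier cannot rescue a masked sample that reads below the cut point, however, because such a sample never reaches it.
- A reader might infer that drug levels are high at most visits. No volume, expected concentration or tolerance limit is given, so high has no defined meaning. At a 10% yardstick only 4 of 8 visits qualify in Arm A.
- A reader might infer that drug is never washed out. Week 36 lies 5 to 8 half-lives after the last active dose, and the protocol itself uses 5 half-lives as its follow-up horizon.

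**Conclusion.** The classification rule omits a variable that is measured at every ADA visit, and that variable is expected to differ about 6.3-fold between arms at Weeks 20, 24, 28 and 36 (4.4 to 14 over the assumed half-lives). The ratio rests on single-dose healthy-volunteer pharmacokinetics and linear decay. Whether it turns into misclassification depends on the assay's drug tolerance, so the size of any bias is unknown and may be zero.

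The per-visit tables from Week 20 are the most exposed. The overall status and the TEAE strata are less exposed for subjects followed to Week 36, and more so for those who leave early for the extension. It would go too far to say that an ADA difference between arms would be an artefact. The supportable statement is that the planned tables could not rule that out. This is an inexpensive improvement to a descriptive analysis, not a flaw in any planned inference.

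**What to change.** In SAP section 10:
1. Take the validated drug-tolerance limit from the bioanalytical laboratory. The cut point already comes from there, and the titre fold increase is already left to assay development.
2. Report a BCP or NCP sample whose same-visit concentration exceeds that limit as inconclusive. Confirmed positives stay positive at any concentration.
3. Show positive, negative and inconclusive counts by visit and arm, with all observed samples as the main denominator. Any percentage of conclusive samples should be supplementary and labelled as biased upward where drug is high, because positives always stay in that denominator while negatives drop out.
4. Class a subject as overall negative only if no post-Baseline sample is confirmed positive and the last sample is at or below the limit. A subject with no confirmed positive who fails the second condition is inconclusive.
5. Use the same three groups in the ADA-stratified TEAE table of SAP section 11.2.3.

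The cost is SAP wording and one derived flag from data already collected. The downsides are fewer subjects classed as negative, and a small third stratum whose membership depends partly on when subjects leave for the extension.
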